### 6.2 Secondary Objective

2. To assess the effect of suvorexant on fatigue and daytime sleepiness in this population

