#### • Fatigue Visual Analogue Scale (VAS-F)

The VAS-F is a 10-cm line that asks subjects to rate fatigue on a scale of 0 (no fatigue) to 100 (fatigue "as bad as it can be") by marking their fatigue level on the line (See appendix). The VAS-F has been validated as a measure of response to therapy in MS fatigue populations (Rammohan et al.2002, Weinshenker et al. 1992). Ratings will be based on their fatigue experience over the previous 1 week.

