#### • Wearable Sleep Monitor (WSM)

A Fitbit device will be worn throughout the study. A 7-night average for screening period will be compared with the final 7-night average for both treatment periods. Outcome measures based on the wearable sleep monitor will include:

- Total minutes asleep
- Minutes awake during time in bed
- Number of awakenings
- Time in bed

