# 13. Data Management and Statistical Analysis

#### **Sample Size Considerations**

This is a prospective, double-blinded, randomized controlled pilot study. The purpose is to test a hypothesis in a preliminary fashion in this population with a specific neurological disease. In our initial statistical plan, the study was underpowered, based on an enrollment target of 30 subjects. We later increased the enrollment to 50 subjects to adequately power the study. We assume that no more than 10% of subjects will withdraw, be lost to follow-up or be dropped for protocol violations, leaving 45 subjects for final analysis. Power calculation is based on a cross-over design. We assume that the true difference in mean Insomnia Severity Index (ISI) between the treatments will be 1.75 units based on the findings of a cross-over trial by Herring et al for treatment effect of suvorexant on ISI in patients with primary insomnia. (Herring et al, 2012) We assume that our cohort with MS with adjustable dose titration (10mg and 20mg) will yield a slightly lower treatment response than that of the Herring cohort at 20mg (-2.0 units). We assume a normal distribution with standard deviation of the difference in the ISI is 4.1, based on normative data from Bastien, et al, who conducted the primary validation study. (Bastien et al, 2001) With these assumptions, the probability (power) is 81 percent that the study will detect a treatment difference at a two-sided 5.000 percent significance level. (PS Power and Sample Size Calculations, version 1.7.15, http://hedwig.mgh.harvard.edu/sample\_size/size.html#cross)

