#### **Statistical Analysis**

Statistical analysis will be performed by a consulting statistician contracted with EvergreenHealth and whose services we have used on recent studies in MS. All data will remain blinded throughout the data analysis and will be un-blinded only in the event of a medical emergency.

Generally, the mean over the week prior to visit 2 (baseline) will be compared to the mean over the final week of Treatment Period 1 and the mean over the final week of Treatment Period 2 for treatment effects. This will be done by treatment arm. Level of significance will be p < 0.05. Minimum drug adherence for per-protocol criteria will be 75%. We plan to do both intention to treat and per-protocol analyses.

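### The p < 0.05 rule is not limited to the ISI: the secondary outcomes have no testing order or descriptive status, and no scale clearly decides the fatigue objective

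*Combined protocol and SAP*

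**What the plan says.** The Introduction and section 11.1 name one primary outcome, the ISI. Section 13 powers the trial on it alone: the calculation assumes that "the true difference in mean Insomnia Severity Index (ISI) between the treatments will be 1.75 units" and that the "standard deviation of the difference in the ISI is 4.1", and it concludes that "the probability (power) is 81 percent" with 45 subjects analysed.

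The Statistical Analysis section then describes in general terms a comparison of baseline with the final week of each treatment period, and adds "Level of significance will be p < 0.05". That sentence names no outcome. The section contains no multiplicity adjustment, no testing order, no dependence of secondary claims on the ISI, and no statement that secondary results are descriptive.

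Section 11.2 lists six secondary measures: sQUAL, sFRESH, MFIS, VAS-F, the wearable sleep monitor and the global impression of change. The monitor entry opens with "Outcome measures based on the wearable sleep monitor will include" and gives four variables, which makes nine results. Section 11.3 is a separate exploratory tier (step count and the Beck inventory).

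The secondary objective in section 6.2 is "To assess the effect of suvorexant on fatigue and daytime sleepiness in this population". Two section 11.2 scales measure fatigue. The MFIS entry describes that scale as well validated and then says its total score serves as the primary efficacy measure. The VAS-F entry says "The VAS-F has been validated as a measure of response to therapy in MS fatigue populations". Section 6.2 does not say which scale decides.

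**The concern.** A significance threshold that names no outcome can be applied to every secondary result. Because the protocol has a separate exploratory tier, the section 11.2 outcomes cannot be assumed to be exploratory. Someone following the plan exactly could therefore face a non-significant ISI and still call the drug significantly better on a monitor variable, a diary item or a fatigue scale, with no rule in the plan against it.

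The fatigue objective is the most exposed. With two validated scales and no stated lead, the one that reaches p < 0.05 can be put forward after the data are seen. The MFIS sentence makes this worse: after a negative ISI it could be cited to present the MFIS as a primary result.

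**Working it through.** **1. The plan's own figure.** Inputs from section 13: difference 1.75, SD of the difference 4.1, 45 analysed (50 less 10%), two-sided 5%.

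- Standard error = 4.1/√45 = 0.611.
- 1.75/0.611 = 2.863.
- Power = Φ(2.863 − 1.960) = 81.7%. The noncentral t version with 44 df gives 80.0%.

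The stated 81% is reproduced. It uses the full two-sided 0.05 on the ISI. Because the ISI is the one designated primary, its 5% error does not depend on how many secondaries are tested.

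**2. Any p < 0.05 among the secondaries, either direction, no true effect, independent.** The formula is 1 − 0.95^k.

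- Nine results: 1 − 0.95^9 = 37.0%.
- Six (monitor counted once): 1 − 0.95^6 = 26.5%.
- Two fatigue scales: 1 − 0.95^2 = 9.75%.
- Ceiling for nine under any dependence: 9 × 0.05 = 45%.

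**3. A false improvement only.** A two-sided 0.05 test errs in the favourable direction 2.5% of the time, so the formula is 1 − 0.975^k.

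- Nine: 1 − 0.975^9 = 20.4%.
- Eight, leaving out time in bed, which has no stated direction of benefit: 1 − 0.975^8 = 18.3%.
- Six: 1 − 0.975^6 = 14.1%.
- Two fatigue scales: 1 − 0.975^2 = 4.9%.

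**4. Correlated outcomes.** The documents give no correlations, so a range is assumed. With normal test statistics sharing a common correlation ρ, and g standard normal, the chance of at least one false improvement is 1 − E[Φ((1.96 − √ρ·g)/√(1−ρ))^k]. The either-direction figure replaces Φ with the probability of lying between −1.96 and 1.96.

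| Assumed ρ | Nine, either direction | Nine, false improvement | Two fatigue scales, either direction | Two fatigue scales, false improvement |
|---|---|---|---|---|
| 0 | 37.0% | 20.4% | 9.75% | 4.9% |
| 0.3 | 32.6% | 16.5% | 9.5% | 4.8% |
| 0.5 | 26.9% | 13.5% | 9.1% | 4.5% |
| 0.7 | 20.2% | 10.1% | 8.3% | 4.2% |
| One test | 5% | 2.5% | 5% | 2.5% |

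**5. Effect of the fix.** If the ISI is tested first at 0.05, and the MFIS total carries confirmatory weight only when the ISI is significant, two cases arise. If neither outcome has an effect, a false confirmatory claim needs a false ISI result, which has a 5% chance. If only the ISI has an effect, the false claim is on the MFIS, at most 5%. The error over both formal claims stays at 5%, and the power in step 1 is unchanged.

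**The case against.** The strongest reply is that this is a self-described pilot, meant to test one hypothesis in a preliminary way. It has labelled primary, secondary and exploratory tiers and a power calculation on the ISI alone. Secondary outcomes are conventionally read as supportive, and one sentence saying so would close the gap. Formal error control over secondaries is partly a matter of preference in such a trial. This lowers the weight of the point and makes a strict gate on the ISI debatable. It does not supply the missing sentence: section 13 also says enrolment was raised so that the study would be adequately powered, and the plan sets a significance level without confining it to the primary.

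Four stronger readings are tempting, and the documents do not support them.

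- A reader might infer that a false secondary finding is likely. The either-direction figure is 37% under independence, which is implausible for overlapping sleep and fatigue measures, and cannot exceed 45%. For a false improvement it is about half the tabulated either-direction figure.
- A reader might infer that the ISI belongs to the unordered family and that its error is inflated. It is the single designated and powered primary, so it is not.
- A reader might infer that the plan explicitly applies p < 0.05 to each outcome. It states the level once and leaves its scope open.
- A reader might infer that the plan allows a fatigue claim on either scale. No passage says so. The MFIS sentence may be meant to choose the total over the subscales, or to make the MFIS the lead on fatigue. As written it does neither clearly.

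**Conclusion.** The point holds as a moderate gap confined to secondary claims. With no true effect on any of nine secondary results, the chance of at least one p < 0.05 in either direction is 37% if independent and about 20–33% at correlations of 0.7–0.3. For a false improvement it is about 20% and 10–17%, against 2.5% for a single outcome. Counting six measures instead of nine gives 26.5% and 14.1% under independence.

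These figures rest on three assumptions: every secondary is judged at two-sided 0.05, the correlations are common and assumed, and each outcome is tested once. The plan also calls for both intention-to-treat and per-protocol analyses without saying which decides. That adds choice not counted here.

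Separately, the MFIS entry in section 11.2 contradicts the Introduction and section 11.1 on which outcome is primary, and the two must be reconciled.

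**What to change.** In the Statistical Analysis section, replace the general significance sentence with a rule to this effect:

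- The two-sided 0.05 level applies to the primary test of the ISI.
- The MFIS total is the single key secondary test of the fatigue objective, at two-sided 0.05. It carries confirmatory weight only if the ISI is significant; otherwise it is reported as supportive.
- All other outcomes in sections 11.2 and 11.3 are reported as estimates with 95% confidence intervals and no claim of significance.

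In the MFIS entry of section 11.2, call the total score the key secondary fatigue measure in place of the primary efficacy measure. Make both changes before unblinding; afterwards they lose most of their value.

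The cost is a few sentences. VAS-F, diary, monitor and global impression results could no longer be called significant, and a fatigue result after a negative ISI would be only supportive. The ISI keeps its full 0.05, so its stated 81% power and N = 50 do not change.

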## 14. Study Management

#### 14.1 Patient stipend

The subjects will be allowed to keep the wearable sleep monitor given at screening. They will also receive a small monetary stipend per completed in-office and phone visit.

### 14.2 Ethics and Good Clinical Practice

This study will be performed according to the principles of Good Clinical Practice [Chapter 2 of the ICH Harmonized Tripartite Guideline for Good Clinical Practice (GCP)], the declaration of Helsinki, and national laws and regulations about clinical studies. The study may not start without written Institutional Review Board/Independent Ethics Committee/Research Ethics Board approval and the written informed consent of the patient.

